### 7.2.11. Results, Changes, and Percentage Change from Baseline in SLICC/ACR Damage Index

The SLICC/ACR damage index is a validated instrument to assess damage, defined as irreversible impairment, continuously persistent for 6 months (ascertained by clinical assessment), occurring since the onset of lupus, and it is based on a weighted scoring system. This index records damage occurring in patients with SLE regardless of cause, with demonstrated content, face, criterion, and discriminant validity. It will be performed on Days 0 and 180.

The analysis of SLICC/ACR Damage Index total score will be performed using an ANCOVA model with change and percentage change from baseline to Day 180 as the dependent variable, treatment group as the factor, and the baseline SLICC/ACR Damage Index total score as a covariate. The SLICC/ACR Damage Index total score is calculated and provided in the clinical database. A missing total SLICC/ACR Damage Index score will not be imputed. Observed results will be presented for the change and percentage change from baseline analysis. The p-value for the difference between the BOS161721 and placebo groups at each nominal visit is based on the F-test.

Descriptive statistics for the SLICC/ACR Damage Index total score will be summarized separately at baseline and Day 180. Change and percentage change from baseline will be summarized at Day 180. The LS Mean estimate, its standard error and 90% CI will be tabulated by treatment group and for the difference between treatment groups (BOS161721 versus placebo) for change and percentage change at Day 180.

In case of medication failure or early withdrawal/discontinuation prior to Day 180, the Day 180 assessment will be considered not evaluable and will not contribute to the analysis at that visit.

These analyses will also be performed for the MAD Phase 1b with the exception of the statistical testing.

Observed SLICC/ACR Damage Index data will be presented in a by-patient listing for all randomized patients. SLICC Criteria for SLE at screening will also be presented in a by-patient listing for all randomized patients.

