  - Note: Treatment with inhaled CS are allowed for the treatment of non-SLE-related indications only (e.g., for asthma).

Sponsor: Boston Pharmaceuticals, Inc.  
Protocol Number: BOS161721-02  
SAP Version and Date: Version 4.0, 23Apr2021

Any other increase from baseline of CS dose or any other systemic use of CS of any kind (including intra-articular and intravenous administration) are not permitted from Day 0 through Day 210 and will result in the patient being considered a medication failure and will be treated as non-responders for the primary efficacy analysis. There is no restriction of CS usage after Day 210.

The determination of medication failures will be reviewed using blinded data and finalized prior to unblinding. Once a patient is determined to be a non-responder, the patient will remain a non-responder for the remainder of the study.

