### 7.2.6.2. Results, Changes, and Percentage Change from Baseline in PGA

The analysis of PGA will be performed separately using an ANCOVA model with change or percentage change from baseline to each nominal visit as the dependent variable, treatment group as the factor, and the corresponding baseline PGA result as a covariate. The p-value for the difference between the BOS161721 and placebo groups at each nominal visit is based on the F-test.

Descriptive statistics for PGA will be summarized separately at baseline and each visit. Change and percentage change from baseline will be summarized at each post-baseline visit. The least squares (LS) mean estimate, its standard error and 90% CI will be tabulated by treatment group and for the difference between treatment groups (BOS161721 versus placebo) for change and percentage change at each visit. In case of missing data, LOCF methods will be implemented as described in Section 5.4 and Table 1 and in Section 7.2.1.

Two separate approaches will be taken based on handling for medication failures and treatment withdrawals:

Sponsor: Boston Pharmaceuticals, Inc.  
Protocol Number: BOS161721-02  
SAP Version and Date: Version 4.0, 23Apr2021

Approach 1: Corresponding to Primary Analysis Methods (Medication Failure LOCF): If a patient is a medication failure, the most recent assessment prior to the medication failure date will be carried forward to all subsequent assessments. In the case of patients who withdraw/discontinue early without prior medication failure, the most recent data on or prior to withdrawal/discontinuation will be carried forward to all subsequent assessments. In case of early withdrawal/discontinuation after Day 180 but before Day 210 such that patient has Day 180 data but is lacking Day 210 data in a patient without medication failure, the Day 180 data will be carried forward to Day 210.

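### Section 7.2.11 drops collected Day 180 SLICC/ACR scores after medication failure or early discontinuation, so the only planned comparison is conditioned on a post-randomisation event

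*SAP*

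**What the plan says.** SAP Version 4.0, Section 7.2.11 (Version 3.0 reads the same) describes the SLICC/ACR damage index as a measure of irreversible impairment and adds: "This index records damage occurring in patients with SLE regardless of cause". On the schedule: "It will be performed on Days 0 and 180". There is therefore a single post-baseline assessment.

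The analysis is an ANCOVA of change and percentage change to Day 180, with treatment as factor and baseline score as covariate. A missing total is not imputed, and "Observed results will be presented for the change and percentage change from baseline analysis". The section then adds: "In case of medication failure or early withdrawal/discontinuation prior to Day 180, the Day 180 assessment will be considered not evaluable". It goes on to spell out what this means for such a score: "and will not contribute to the analysis at that visit".

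No second analysis of this endpoint is described. The removed scores appear only in a listing: "Observed SLICC/ACR Damage Index data will be presented in a by-patient listing for all randomized patients".

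For change in PGA, Section 7.2.6.2 says: "Two separate approaches will be taken based on handling for medication failures and treatment withdrawals". Approach 1 carries the last value before the failure or withdrawal forward; Approach 2 excludes. The CLASI, ACR-28 and SLEDAI-2K change sections adopt the same pair (the last two cite 7.2.6.1, although the approaches stand in 7.2.6.2). Section 7.2.11 contains only the exclusion and refers to neither section.

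**The concern.** Medication failure and early discontinuation happen after randomisation and may depend on treatment. Section 6.1 has the full analysis set analysed by randomised arm, but an ANCOVA restricted to patients free of these events compares subsets that the treatment may itself have shaped. If the proportion removed differs by arm, and removed patients accrue damage at a different rate from the rest, the estimated difference is biased. If the proportions are equal, patients and precision are still lost.

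The exclusion also fits this endpoint poorly. After rescue treatment, a disease activity score may no longer reflect study drug alone, so a plan may have reason to set it aside. An index of irreversible damage that counts events whatever their cause remains a valid measurement of that patient's damage after a prohibited drug or extra steroid.

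At stake is the interpretation of one secondary endpoint. The primary SRI-4 test and the sample size are untouched.

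**Working it through.** **1. Does the sentence reach scores that exist?** Yes. A score never collected is already out, because missing totals are not imputed and observed results are used. What the sentence adds is the removal of scores that were collected.

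**2. What triggers the exclusion?** Section 7.1.1 defines medication failure as use of prohibited medication or unallowable corticosteroid use. The latter includes "Any other increase from baseline of CS dose or any other systemic use of CS of any kind", but also as-needed topical steroids and any change in oral dose between Day 150 and Day 210. A patient whose oral dose changes shortly before the Day 180 visit thus loses the damage score taken at that visit.

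**3. Would Approach 1 of Section 7.2.6.2 repair it?** No. The only assessment before Day 180 is Day 0. Carrying it forward gives change = baseline - baseline = 0 for every such patient, whatever was observed.

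**4. How large could the effect be?** The SAP states no figure for this endpoint that could be reproduced. Its only sample-size figure, 96 evaluable patients for SRI-4 (Section 3.3), reproduces as 64 + 32 with the continuity-corrected formula; I use it only for arm sizes at 2:1.

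Assumed, not in the SAP:
- failure proportions f_A (active) and f_P (placebo);
- mean damage increase m0 without failure and m1 with failure, the same in both arms, so treatment has no effect within failure status;
- a Day 180 score for all 96 patients, and a common SD that the exclusion leaves unchanged.

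Formulas:
- arm mean, all scores = (1 - f) × m0 + f × m1
- difference, all scores = (f_A - f_P) × (m1 - m0)
- difference after exclusion = m0 - m0 = 0
- SE ratio = √[(1/n_A + 1/n_P) / (1/64 + 1/32)], with n_A = 64(1 - f_A) and n_P = 32(1 - f_P)

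Worked case, f_A = 10%, f_P = 30%, m0 = 0.05, m1 = 0.20:
- active: 0.90 × 0.05 + 0.10 × 0.20 = 0.065
- placebo: 0.70 × 0.05 + 0.30 × 0.20 = 0.095
- difference: 0.065 - 0.095 = -0.030; after exclusion 0
- share of total damage removed: 0.020/0.065 = 31% (active), 0.060/0.095 = 63% (placebo)
- patients left: 57.6 and 22.4; SE ratio √[(1/57.6 + 1/22.4)/(1/64 + 1/32)] = 1.15

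| f_A / f_P | m0 / m1 | Difference, all scores | After exclusion | SE ratio |
|---|---|---|---|---|
| 10% / 20% | 0.02 / 0.10 | -0.008 | 0 | 1.10 |
| 10% / 20% | 0.05 / 0.20 | -0.015 | 0 | 1.10 |
| 10% / 30% | 0.05 / 0.20 | -0.030 | 0 | 1.15 |
| 15% / 40% | 0.05 / 0.30 | -0.0625 | 0 | 1.23 |
| 10% / 10% | any of these | 0 | 0 | 1.05 |
| 30% / 30% | any of these | 0 | 0 | 1.20 |

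The zeros after exclusion follow from assuming no treatment effect within failure status. The table shows how the rule can act. It does not estimate what will happen in this trial.

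**The case against.** Several objections have force.

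- **Setting aside data after rescue is a recognisable choice of question.** Rescue may add damage or prevent some, so it would be wrong to say there is no confounding to remove. That stands. But dropping the patients does not estimate what would have happened without rescue; it describes those who did not need it. It does not justify having only this analysis.
- **Little new damage can appear.** Section 7.2.11 requires impairment to persist for six months. At the Section 5.2 conversion that is 6 × 30.4375 = 182.6 days, so impairment that begins after a failure cannot normally qualify by Day 180. Items scored as having ever occurred (Section 13.6: cataract, cerebrovascular accident, myocardial infarction) can still newly score. This limits the size and is the main reason the point is minor.
- **The other endpoints are not handled so differently.** Neither approach in Section 7.2.6.2 uses scores observed after failure, and percent steroid reduction (Section 7.2.4.3) also only excludes failures. Both are correct. The contrast is narrower: PGA, CLASI, ACR-28 and SLEDAI-2K change scores have one approach that keeps such patients in the analysis.
- **Failures are visible elsewhere.** Section 7.2.12 compares their proportion and timing, and all SLICC/ACR scores are listed. True, but neither is a comparison of damage.

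A reader might infer that the rule removes the sickest and most steroid-exposed patients and so hides a benefit of treatment. The SAP does not support that. Failure also covers as-needed topical steroids and any oral dose change from Day 150 on, including a reduction. The SAP gives no severity, steroid exposure or damage by failure status, so even the direction of bias is open.

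**Conclusion.** The point holds, as a minor one. The only planned SLICC/ACR comparison leaves out collected Day 180 scores because of a post-randomisation event that does not invalidate them.

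Bias requires two things together: failure or discontinuation rates that differ by arm, and damage accrual that differs between excluded and retained patients. Neither is known from the SAP. Over the assumed values tried, a difference of -0.008 to -0.0625 points is reduced to 0; with equal failure rates of 10% to 30% there is no bias and the standard error rises by 5% to 20%. These figures rest on invented inputs and have no SD to scale them, so they should not be quoted as an expected effect.

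The endpoint is one of many secondaries, without its own power statement and without multiplicity adjustment (Section 4.3).

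**What to change.** Replace the exclusion sentence in Section 7.2.11 with text along these lines: *The main ANCOVA includes all observed Day 180 SLICC/ACR scores obtained at least 159 days after first dose, in the FAS by randomised arm, regardless of medication failure or treatment discontinuation. A supportive ANCOVA excludes patients with medication failure or early withdrawal/discontinuation before Day 180. The number excluded is reported by arm.*

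The 159-day limit is the one Section 7.1.1 (Out of Window Assessments) already sets for nominal Day 180 assessments, a visit labelled in the database as Day 180/End of Treatment. It keeps much earlier end-of-treatment scores from counting as Day 180. Approach 1 of Section 7.2.6.2 should not be borrowed, since it would force zero change.

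The cost is one SAP edit and one additional analysis of scores already collected. Patients with no Day 180 score remain missing, so the result is still not a complete randomised comparison. How many discontinued patients have a score depends on the protocol's visit rules, which are not shown here; the main gain is from medication failures who stayed in the study.

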### 7.2.12. Medication Failure

#### 7.2.12.1. Proportion of Patients with Medication Failures

Patients who received prohibited medications or had unallowable CS usage as described in Section 4.6 of the study protocol will be considered “medication failures” and will be treated as non-responders at time points on and following the first date of prohibited medication or unallowable CS usage for the primary efficacy analysis and selected sensitivity and secondary efficacy analyses. The determination of medication failures and medication failure dates will be reviewed using blinded data and finalized prior to unblinding.

Sponsor: Boston Pharmaceuticals, Inc.  
Protocol Number: BOS161721-02  
SAP Version and Date: Version 4.0, 23Apr2021

The number and proportion of patients with medication failures will be summarized by study phase and treatment group in the FAS overall and by visit. A patient will be counted as a medication failure at each visit occurring on and after the date in which a patient is considered a medication failure. Statistical methods described in Section 7.1.1 will be implemented for observed data only. LOCF and missing data imputation will not be performed.

The denominator is the number of patients in FAS (overall analysis) and the number of patients with non-missing visit data (for the by visit analysis).

Statistical testing data will be omitted from MAD Phase 1b treatment group displays.

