**Table 2**

| Analysis   | Analysis Population | Criteria   |
|--|---------------------|--|
| Primary Analysis

LOCF for missing data,
Medication
Failures=Non-Responder | FAS                 | 
The primary analysis of the primary efficacy endpoint will be performed based on LOCF methods for missing data.
 
 
(1) Medication failures are considered non-responders on and after the date of medication failure
 
(2) Early withdrawals/discontinuations prior to study day 159 will be considered non-responders after the date of early withdrawal/discontinuation
 
 |

|  |     |  |
|--|-----|--|
|  |     | 
 
a. If patient is a medication failure prior to withdrawal/discontinuation, patient will be considered a non-responder on and after the date of medication failure.
 
b. In case of early withdrawal/discontinuation after study day 159 but before Day 210 such that patient has Day 180 data but is lacking Day 210 data in a patient without medication failure, the Day 180 data will be carried forward to Day 210.
 
 
(3) Patients with missing Day 180 and Day 210 data without prior medication failure and without early withdrawal/discontinuation prior to study day 159 are considered not evaluable and are excluded from analysis
  |

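### The by-visit medication-failure rate carries failure forward but counts only patients with data at that visit, so it can reflect who stayed rather than who failed

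*SAP*

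**What the plan says.** SAP version 4.0, Section 7.2.12.1, plans the proportion of patients with medication failure both overall and by visit, by study phase and treatment group, in the FAS.

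- **Numerator by visit.** "A patient will be counted as a medication failure at each visit occurring on and after the date" of failure. The status is never reversed. Section 7.1.1, under Evaluability/Non-Responders, takes the same line for response: "Once a patient is determined to be a non-responder, the patient will remain a non-responder for the remainder of the study".
- **Denominators.** For the overall figure, "The denominator is the number of patients in FAS (overall analysis"). For each visit it is "the number of patients with non-missing visit data (for the by visit analysis").
- **Data basis and testing.** "Statistical methods described in Section 7.1.1 will be implemented for observed data only", and "LOCF and missing data imputation will not be performed". The methods of Section 7.1.1 are a Pearson chi-square test, or Fisher's exact test when an expected count is below 5, with a 90% CI for the difference. Testing applies to Phase 2 only.
- **Exit after failure is foreseen.** Table 2 has a rule for it in the primary analysis: "If patient is a medication failure prior to withdrawal/discontinuation, patient will be considered a non-responder on and after the date of medication failure".
- **Companion analysis.** Section 7.2.12.2 plans Kaplan-Meier estimates and curves, a log-rank test and a Cox hazard ratio for TTMF. In Table 4 a failure is an event dated from the medication record, and a withdrawal without failure is censored.

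**The concern.** A status that is permanent once reached has a natural by-visit summary: the proportion who have reached it by that day. That proportion cannot go down. Section 7.2.12.1 carries the status forward but then evaluates it only in patients who have data at the visit. A failed patient who has left the study has no later visit data, so the failure disappears from the display.

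The restriction is also unnecessary. Whether a patient had failed by a given day is known from the failure date, which is settled under blinded review, and does not depend on attending the visit. Keeping a past failure in the count imputes nothing.

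At stake are the by-visit rates, their confidence intervals and their between-arm p-values. If failed patients leave at different rates in the two arms, the comparison picks up that difference in retention. The by-visit table can also point a different way from the overall FAS proportion and the TTMF curve in the same report.

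**Working it through.** The SAP states no expected medication-failure or withdrawal rate, so there is no plan figure to reproduce. The failure and exit numbers below are assumptions. Only the arm sizes come from the SAP: Section 3.3 gives 96 evaluable patients at 2:1, hence 96 × 2/3 = 64 active and 96 × 1/3 = 32 placebo.

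**Formula as written.** By-visit rate = (failed by that date and with data at the visit) / (all with data at the visit). The reference is (failed by that date) / FAS.

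**One arm.** Assume 13 of 64 active patients fail by Day 120, none later. The reference is 13/64 = 20.3% at Day 120 and at Day 210, whoever leaves. The 64 − 13 = 51 others are non-failed.

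| Leave before Day 210 | Day 210 rate as written |
|---|---|
| nobody | 13/64 = 20.3% |
| 3 failed (about 25%) | 10/61 = 16.4% |
| 6 failed (about 50%) | 7/58 = 12.1% |
| 10 failed (about 75%) | 3/54 = 5.6% |
| 3 failed and 8 non-failed (about 15% of 51) | 10/53 = 18.9% |
| 6 failed and 8 non-failed | 7/50 = 14.0% |
| 10 failed and 8 non-failed | 3/46 = 6.5% |
| 2 failed and 8 non-failed (about 15% of each) | 11/54 = 20.4% |
| 8 non-failed only | 13/56 = 23.2% |

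The rate falls only when failed patients leave proportionately faster than the rest. It is about unchanged when both leave at the same rate, and it rises when the non-failed leave faster.

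**Two arms.** Assume the same true failure proportion in both: 16/64 = 25% and 8/32 = 25%. Suppose 4 failed active and 6 failed placebo patients leave, and nobody else does.

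- Active: (16 − 4)/(64 − 4) = 12/60 = 20.0%.
- Placebo: (8 − 6)/(32 − 6) = 2/26 = 7.7%.
- Displayed difference: 20.0 − 7.7 = 12.3 percentage points, against a true difference of zero.

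The smallest expected count is 26 × 14/86 = 4.23, below 5, so Section 7.1.1 calls for Fisher's exact test. It gives p = 0.21, which is not significant at the 10% level. The example shows a biased estimate, not a false positive.

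**The other reading of the numerator.** If departed failures were kept in the numerator over attendees only, the numerator would no longer be a subset of the denominator. With 6 of the 13 failed gone, the rate would be 13/58 = 22.4%; with all 13 gone, 13/51 = 25.5%. Both overstate 20.3%. The observed-data wording favours the first reading, but the denominator does not work under either.

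**The case against.** The strongest reply is that the by-visit figure is coherent as a cross-sectional quantity: among patients seen at a visit, the share who have already failed. The SAP does not call it cumulative, and it uses attendee denominators elsewhere, for example for BILAG flares by visit (Section 7.2.5). The endpoint list in Section 2.2 names the proportion with medication failures without a visit qualifier, whereas it attaches one to SRI-4, SRI-5 and SRI-6. The listed endpoint is therefore most naturally the overall proportion, which already has the full FAS as denominator. TTMF shows cumulative failure over time without this flaw. Finally, nothing in the SAP says that failed patients tend to leave.

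Most of this stands, and it sets the size of the point. A reader might infer that the medication-failure endpoint as a whole, or even the primary analysis, is biased. The documents do not support that: the overall proportion uses the FAS, TTMF keeps each failure as an event, and failed patients remain non-responders for SRI-4. A reader might also infer that the by-visit rate must fall, or must disagree with the other two analyses. It can, but need not; with no missing visits, the rate as written equals the FAS-based rate at every visit.

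What does not stand is the cross-sectional defence of a between-arm test. After exits, the arms being compared are no longer the randomised groups, and the outcome itself may influence who is left.

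**Conclusion.** The point holds for the by-visit medication-failure display and its Phase 2 tests, and for nothing else. Section 7.2.12.1 fixes a denominator that lets known failures vanish when patients leave, so the rates and comparisons can reflect retention after failure.

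The size cannot be determined from the SAP. Under the assumptions above (20.3% failed by Day 120, no later failures), the Day 210 figure ranges from 5.6% with about three quarters of the failed gone to 23.2% with only 15% of the non-failed gone. With equal exit rates there is essentially no distortion. A large fall such as 20.3% to 5.6% requires heavy and selective exit of failed patients and should be read as an extreme case, not a forecast. Because sound analyses of the same outcome are already planned, this is a correction worth making to a supporting table rather than a threat to the trial's conclusions.

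**What to change.** **Preferred.** Replace the attendee-based by-visit proportion with the Kaplan-Meier cumulative failure estimate by arm, with 90% CI, at each nominal visit day, taken from the Section 7.2.12.2 analysis. It keeps every failure after exit and censors patients who withdraw without failing. Between-arm inference then rests on the log-rank test and hazard ratio already planned. The cost is a few extra rows of output and no new data. It relies on censoring being unrelated to the risk of failure, as the planned TTMF analysis already does. Because TTMF counts the randomisation date as day 1, a patient randomised on Day 0 reaches nominal Day 210 at TTMF = 211; the programming note should say so.

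**Alternative.** Use the FAS as denominator at every visit, and count every patient whose adjudicated failure date is on or before the actual visit date, or the scheduled date if the visit was not attended. This needs a rule for scheduled dates of unattended visits. It also counts patients who withdraw without failing as non-failures at all later visits, which should be stated in a footnote.

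The overall FAS proportion in Section 7.2.12.1 needs no change.
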